7.3 Disposition of Subjects

Trial information will be presented for all screened subjects, including the date the first subject signed the informed consent form, the date of the first subject's first visit, the date of the last subject's last visit, the date of first subject's first vaccination, the date of last subject's first vaccination, the date of first subject's second vaccination, the date of last subject's second vaccination, the Medical Dictionary for Regulatory Activities (MedDRA) version, the World Health Organization Drug Dictionary (WHODrug) version, and the SAS version used for analysis.

Disposition of all screened subjects will be summarized descriptively, including a summary of the number of screened subjects, the number of randomized subjects and the primary reason for not being eligible for randomization. The number of screen failures and their characteristics will also be summarized.

Disposition for all randomized subjects will be summarized by trial group. Disposition categories include:

- Number of subjects randomized by trial site.
- Number of subjects randomized, but not vaccinated (including primary reason for being randomized, but not vaccinated).
- Number of subjects in the Randomized Set, Safety Set, FAS, and PPS.
- Number of subjects who completed the vaccine regimen/trial visits.
- Number of subjects who prematurely discontinued the vaccine regimen/trial visits.
- Primary reason for premature discontinuation of the vaccine regimen/trial visits.

Additionally, significant protocol deviations as captured on the CRF will be summarized based on the Safety Set.

7.4 Demographic and Other Baseline Characteristics

Age, gender, race, and other Baseline characteristics will be summarized descriptively based on the Safety Set, FAS and PPS.

7.5 Medical History and Concurrent Medical Conditions

Medical history and concurrent medical conditions will be coded according to the MedDRA coding system. The version of the dictionary used will be specified in the CSR.

A medical history is defined as any significant condition/disease that stopped at or prior to first dose of IP. A concurrent medical condition is defined as any significant condition/disease that is ongoing at the time the first dose of IP is administered.

Summary tables will be provided by SOC and PT based on the Safety Set.

7.6 Medication History and Concomitant Medications

Medication history, vaccine history, concomitant medications, and concomitant vaccines will be coded according to WHODrug. The version of the dictionary used will be specified in the CSR.

A prior medication/vaccine (history) is any medication/vaccine which intake was stopped before first dose of IP. A concomitant medication/vaccine is any medication/vaccine ongoing at the time the first dose of IP is administered, or taken/administered on/after the first dose of IP.

Summary tables for medication history and concomitant medications will be provided by Anatomical Therapeutic Chemical class level 2 and preferred medication name. Vaccine history and concomitant vaccines will be summarized by vaccine type and name as recorded on the CRF. Summaries will be provided based on the Safety Set.

7.7 Investigational Product Exposure and Compliance

The Investigator records all injections of the IP given to the subject on the CRF.

Investigational product compliance will be summarized by trial group (including a separate group of subjects who received different IPs at first and second vaccination [if any]) for the Safety Set presenting the number and percentage of subjects receiving:

- 1) First vaccination only
- 2) Both vaccinations

The duration of follow-up after the first dose of IP (defined as the number of days from first vaccination to end of the trial) will be summarized by trial group for the Safety Set as a continuous variable (number of subjects [n], mean, SD, median, minimum, and maximum), and also as categorical variable (frequency and percentage of subjects) for the following intervals: 1 – 30 days, 31 – 90 days, 91 – 120 days, 121 – 270 days, >270 days. Additionally, the duration of follow-up after the second dose of IP (defined as the number of days from second vaccination to end of the trial) will be summarized in a similar way as a continuous variable and also as categorical variable for the following intervals: 1 – 30 days, 31 – 90 days, 91 – 180 days, >180 days.

7.8 Efficacy Analysis

Not applicable.

7.9 Pharmacokinetic/Pharmacodynamic Analysis

Not applicable.

7.10 Other Outcomes

7.10.1 Primary Immunogenicity Analyses

The primary immunogenicity endpoint of this trial is the GMTs of dengue neutralizing antibodies (derived from dengue MNT₅₀ results) for each of the 4 dengue serotypes 1 month post second dose (ie, Day 120 [M4]).

The number of subjects with non-missing assessments, geometric mean with 95% CI, geometric SD, median, minimum and maximum will be presented for neutralizing antibody titers for each dengue serotype by trial group. GMTs will be calculated as anti-logarithm of $\sum(\log \text{transformed titer}/n)$, where n is the number of subjects with titer information. The 95% CI for GMTs will be calculated as the anti-log transformation of upper and lower limits for a 2-sided CI of the mean of the log-transformed titers (based on student's t-distribution).

The primary immunogenicity endpoint will be summarized by trial group based on the PPS. A supportive analysis will be provided using the FAS.

7.10.2 Secondary Immunogenicity Analyses

The secondary immunogenicity endpoints of this trial are:

- GMTs of neutralizing antibodies (MNT₅₀) for each of the 4 dengue serotypes at 6 months post second dose (ie, Day 270 [M9]).
- Seropositivity rates (% of subjects seropositive) for each of the 4 dengue serotypes at 1 month and 6 months post second dose (ie, Day 120 [M4]) and Day 270 [M9], respectively).
- Seropositivity rates (% of subjects seropositive) for multiple (2, 3, or 4) dengue serotypes at 1 month and 6 months post second dose (ie, Day 120 [M4]) and Day 270 [M9], respectively).

GMTs of dengue neutralizing antibodies (derived from dengue MNT₅₀ results) at 6 months post second dose will be analyzed in analogy to the primary immunogenicity endpoint.

For the seropositivity rates for each dengue serotype, the percentage of subjects seropositive along with exact 2-sided 95% CI will be presented by trial group and visit. The exact 2-sided 95% CI of seropositivity rate will be calculated based on Clopper-Pearson method [4]. Seropositivity is defined as a reciprocal neutralizing titer ≥ 10 .

Seropositivity rates for multiple dengue serotypes will be analyzed in analogy to the seropositivity rates for each dengue serotype, as described above, and will include the percentage of subjects with:

- monovalent seropositivity (seropositive for only 1 of the 4 dengue serotypes),
- bivalent seropositivity (seropositive for any 2 of the 4 dengue serotypes),
- trivalent seropositivity (seropositive for any 3 of the 4 dengue serotypes),
- tetravalent seropositivity (seropositive for all 4 dengue serotypes),

- at least bivalent seropositivity (seropositive for ≥ 2 dengue serotypes),
- at least trivalent seropositivity (seropositive for ≥ 3 dengue serotypes)

The secondary immunogenicity endpoints will be summarized by trial group based on the PPS. Supportive analyses will be provided based on the FAS.

In addition, GMTs (including 95% CIs) over time (all visits) and reverse cumulative distribution curves (all visits except baseline) will be plotted (line plots) by dengue serotype, trial group and visit based on the PPS. Seropositivity rates will be graphically presented by dengue serotype, for at least trivalent, and for tetravalent seropositivity, and by trial group and visit using bar graphs including the percentage of subjects seropositive and corresponding 95% CIs.

7.11 Safety Analysis

All summaries of safety data will be based on subjects in the Safety Set.

7.11.1 Adverse Events

Unless otherwise specified, AEs will be summarized by trial group after first trial vaccination, second trial vaccination, and any trial vaccination.

Reactogenicity (Solicited AEs)

Solicited AEs are collected for at least 30 min after each vaccination at the site (in-clinic assessment). In addition, subjects are provided with a diary card for the recording of solicited local (injection site) AEs, including injection site pain, injection site erythema, and injection site swelling, for 7 days following vaccination (day of vaccination + 6 days). Subjects are also provided with a diary card for the recording of solicited systemic AEs (fever, headache, asthenia, malaise, and myalgia) for 14 days following vaccination (day of vaccination + 13 days). For the local (injection site) AEs erythema and swelling, the subject/the subject's legally authorized representative (LAR) will record the length of the longest diameter in mm. However, for the analysis these data will be displayed in cm. For the systemic AE fever, the subject/the subject's LAR will record the body temperature in either $^{\circ}\text{F}$ or $^{\circ}\text{C}$. For the analysis, all data will be displayed in $^{\circ}\text{C}$. Severity grades for erythema and swelling will be derived from the recorded diameters, and fever will be presented using the proposed temperature increments published by the Brighton Collaboration Fever Working Group [5]. Details of solicited local (injection site) and systemic AEs, and severity of solicited safety parameters are given in [Appendix B](#).

Missing data for solicited AEs will not be imputed unless otherwise specified in Section [7.1.3](#). For each trial group and solicited AE, the denominator for the percentage will exclude subjects with completely missing data (ie, subject does not have at least 1 recorded result [ie, none, mild, moderate, or severe]) for the solicited AE in the period being summarized.

For each solicited AE, the number and the percentage of subjects reporting an event will be summarized by event severity for the following intervals post-vaccination:

- 30 minutes (in-clinic assessment of solicited local [injection site] and systemic AEs – analyzed separately from diary-recorded solicited AEs)
- Within 7 days (solicited local [injection site] AEs)
- Within 14 days (solicited systemic AEs)
- Days 1 – 7 (daily, solicited local [injection site] AEs)
- Days 1 – 14 (daily, solicited systemic AEs)
- Days 1 – 3 and Days 4 – 7 (solicited local [injection site] AEs)
- Days 1 – 7 and Days 8 – 14 (solicited systemic AEs)

For subjects with more than 1 episode of the same event, the maximum severity will be used for tabulations.

For solicited systemic AEs, the number and percentage of subjects will also be summarized by relationship to IP (assessed by the Investigator) for the following intervals post-vaccination:

- 30 minutes
- Within 14 days

Subjects will only be counted once if the subject has more than 1 episode of the same event. In the case where the subject has both related and unrelated solicited systemic AEs, the subject will be counted under the related category. All solicited local (injection site) AEs are considered as related to IP.

A summary of the day of first onset of each event and the number of days subjects reported each event will be presented post-vaccination. The number of days a subject reported each event is calculated as the total of all days the subject reported the event, regardless of whether the event was reported on consecutive days.

An overview table for solicited AEs post-vaccination will be provided including:

- 30 minutes in-clinic assessment (solicited local [injection site] and systemic AEs combined)
- Solicited AEs (solicited local [injection site] and systemic AEs combined)
- Solicited local [injection site] AEs
- Solicited systemic AEs (overall and by relationship to IP)
- Prolonged solicited AEs (overall and for solicited local [injection site] and systemic AEs separately)

Prolonged solicited AEs that continue beyond Day 7 (for local [injection site] AEs) or Day 14 (for systemic AEs) will be captured on the AE CRF with appropriate indication (“continued solicited AE”). These prolonged solicited AEs will be presented in separate listings and will not be included in any unsolicited AE summary or listing.

Unsolicited AEs

Unsolicited AEs will be assessed for 28 days following administration of each trial dose (day of vaccination + 27 subsequent days). MAAEs, SAEs and AEs leading to IP withdrawal or trial discontinuation will be collected from first trial dose (Day 1 [M0]) until the end of the trial (Day 270 [M9]). Unsolicited AEs, MAAEs, SAEs, and AEs leading to IP withdrawal or trial discontinuation will be coded according to the current version of MedDRA and summarized by SOC and PT.

In general, the number of events, number of subjects, and the percentage of subjects will be tabulated by trial group at each of the following levels: overall summary (any AEs/subjects with any AEs) and by SOC and PT. Subjects reporting more than 1 occurrence for the term (level) being summarized will be counted only once in the number/percentage of subjects. Percentages will be based on the number of subjects in the Safety Set who received the respective trial dose.

Unsolicited AEs up to 28 days post-vaccination will be summarized as follows:

- By SOC and PT;
- By SOC and PT including events with frequency greater than 2% in any trial group;
- By SOC and PT including non-serious events with frequency greater than 2% in any trial group (including a separate group of subjects who received different IPs at first and second vaccination [if any]);
- By SOC and PT for IP related events;
- By SOC and PT for IP related events with frequency greater than 2% in any trial group;
- By SOC, PT, and severity (mild, moderate, severe).

MAAEs post-vaccination throughout the trial duration will be summarized as follows:

- By SOC and PT;
- By SOC and PT for IP related events;
- By SOC, PT, and severity (mild, moderate, severe).

SAEs post-vaccination throughout the trial duration will be summarized as follows:

- By SOC and PT (including a separate group of subjects who received different IPs at first and second vaccination [if any]);
- By SOC and PT for IP related events.

AEs leading to IP withdrawal or trial discontinuation post-vaccination throughout the trial duration will be summarized as follows:

- By SOC and PT (including a separate group of subjects who received different IPs at first and second vaccination [if any]);

- By SOC and PT for IP related events.

In addition, overview tables by trial group will be generated for unsolicited AEs (collected up to 28 days post-vaccination), SAEs, MAAEs and AEs leading to IP withdrawal or trial discontinuation including the variables as outlined in [Table 7.d](#).

Table 7.d Overview of Unsolicited Adverse Events

	All AEs (28 days post- vaccination)	SAEs	MAAEs	AEs leading to IP withdrawal and/or trial discontinuation
Relationship to IP	✓	✓	✓	✓
Relationship to trial procedure	✓	✓	✓	✓
Severity	✓	✓	✓	✓
AEs leading to IP withdrawal and/or trial discontinuation	✓	✓	✓	
AEs leading to IP withdrawal	✓	✓	✓	✓
AEs leading to trial discontinuation	✓	✓	✓	✓
MAAEs	✓			✓
SAEs and Non-serious AEs	✓			✓
Deaths	✓	✓		✓

Subject mappings (ie, list of subject numbers in each category of SOC and PT, and each trial group) will be provided for unsolicited AEs, SAEs, MAAEs and AEs leading to IP withdrawal or trial discontinuation.

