10.4.3 Collection and Reporting of Medically Attended Adverse Events

MAAEs occurring from first vaccination at Day 1 (M0) until the end of the trial (Day 270 [M9]) will be collected during site visits by interview and must be recorded as an AE on the AE eCRF.

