4.2 Secondary Objectives

Immunogenicity:

- To describe the persistence of the immune response at 6 months post second dose of TDV or placebo in dengue-naïve adolescent subjects.
- To describe the seropositivity rates for all dengue serotypes at 1 month and 6 months post second dose of TDV or placebo in dengue-naïve adolescent subjects, where seropositivity is defined as a reciprocal neutralizing titer ≥ 10 .

Safety:

- To describe the safety profile following a first and second dose of TDV or placebo at Day 1 (Month 0 [M0]) and Day 90 (Month 3 [M3]), respectively.

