4.4 Study Design

This is a randomized, double-blind, placebo-controlled, phase 3 trial in 400 healthy adolescent subjects aged 12 to 17 years in a non-endemic country(ies) for dengue with 2 parallel groups to investigate the immunogenicity and safety of subcutaneous (SC) administration of a 2 dose regimen of TDV.

[figure not shown]
Subjects will be randomized in a 3:1 ratio (TDV [300 subjects]: placebo [100 subjects]) using an interactive response technology, as follows:

- Group 1: SC administration of TDV at Day 1 (M0) and Day 90 (M3).
- Group 2: SC administration of placebo at Day 1 (M0) and Day 90 (M3).

The trial duration for each subject will be approximately 270 days (9 months) including trial dose administration (Day 1 [M0] and Day 90 [M3]) and follow-up through Day 270 [Month 9 (M9)].

A schematic of the trial design is included in [Figure 4.a](#). A schedule of trial procedures is provided in [Appendix A](#).

Figure 4.a Schematic of Trial Design

M=Month, V=Visit

Immunogenicity evaluation:

Dengue neutralizing antibodies (microneutralization test 50% [MNT₅₀]) will be measured using blood samples collected from all subjects at pre-first dose (Day 1 [M0]), and at 1 month and 6 months post second dose (Day 120 [Month 4 (M4)]) and Day 270 [M9], respectively).

Safety evaluation:

- Diary cards will be distributed for the recording of:
 - Solicited local (injection site) adverse events (AE) for 7 days following each TDV/placebo dose on Day 1 (M0) and Day 90 (M3) (day of vaccination+6 subsequent days). These will include: injection site pain, injection site erythema, and injection site swelling.
 - Solicited systemic AEs for 14 days following each TDV/placebo dose on Day 1 (M0) and Day 90 (M3) (day of vaccination+13 subsequent days). These will include: fever, headache, asthenia, malaise, and myalgia.
- Unsolicited AEs for 28 days following each TDV/placebo dose on Day 1 (M0) and Day 90 (M3) (day of vaccination+27 subsequent days).
- Serious adverse events (SAE) and medically attended adverse events (MAAE) for the trial duration. MAAEs are defined as AEs leading to a medical visit to or by a healthcare professional, including visits to an emergency department, but not fulfilling seriousness criteria.

Data collection will be by electronic Case Report Form (CRF).

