5.2 Secondary Endpoints

Immunogenicity:

- GMTs of neutralizing antibodies (MNT₅₀) for each of the 4 dengue serotypes at 6 months post second dose (Day 270 [M9]).
- Seropositivity rates (% of subjects seropositive) for each of the 4 dengue serotypes at 1 month and 6 months post second dose (Day 120 [M4]) and Day 270 [M9], respectively).
- Seropositivity rates (% of subjects seropositive) for multiple (2, 3, or 4) dengue serotypes at 1 month and 6 months post second dose (Day 120 [M4]) and Day 270 [M9], respectively).

Note: Seropositivity is defined as a reciprocal neutralizing titer ≥ 10 .

Safety:

- Frequency and severity of solicited local (injection site) AEs for 7 days (day of vaccination+6 subsequent days) and solicited systemic AEs for 14 days (day of vaccination+13 subsequent days) after each TDV/placebo dose on Day 1 (M0) and Day 90 (M3).
- Percentage of subjects with any unsolicited AEs for 28 days (day of vaccination+27 subsequent days) after each TDV/placebo dose on Day 1 (M0) and Day 90 (M3).
- Percentage of subjects with MAAEs and SAEs and throughout the trial.

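### By-dose percentages for MAAEs and SAEs would cover about 89 days after dose 1 and about 180 after dose 2, so the two columns are not comparable

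*SAP*

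**What the plan says.** SAP 7.11.1 opens with a default for all adverse events, which holds unless something else is specified: "AEs will be summarized by trial group after first trial vaccination, second trial vaccination, and any trial vaccination". Under the Unsolicited AEs heading it sets the denominator: "Percentages will be based on the number of subjects in the Safety Set who received the respective trial dose". That is a count of subjects; no person-time enters.

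The section then gives each family of events its period. Unsolicited AEs are tabulated up to 28 days after vaccination. For MAAEs the lead-in is "MAAEs post-vaccination throughout the trial duration will be summarized as follows". SAEs, and AEs leading to withdrawal of the investigational product (IP) or trial discontinuation, have the same lead-in. All three are collected from the first dose to Day 270. Protocol 10.4.3 adds that MAAEs "will be collected during site visits by interview and must be recorded as an AE on the AE eCRF".

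Three other places bear on the point:

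- **Objective and endpoint.** The safety objective in SAP 4.2 is "To describe the safety profile following a first and second dose of TDV or placebo". The endpoint in SAP 5.2 is not per dose: "Percentage of subjects with MAAEs and SAEs and throughout the trial".
- **Overview table.** In SAP Table 7.d, the column for all AEs within 28 days has ticked rows for MAAEs and for serious and non-serious AEs.
- **Follow-up.** SAP 7.7 summarizes follow-up after the first and after the second dose, each counted from that dose to the end of the trial.

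**The concern.** A first-dose and second-dose layout is sound when both columns cover the same number of days. That is so for solicited local AEs (7 days), solicited systemic AEs (14 days) and unsolicited AEs (28 days). It is not so for events collected over the whole trial: the first-dose period ends when dose 2 is given, and the second-dose period runs to the final visit.

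Because the safety objective names the first and second dose, readers will set the two columns side by side. For MAAEs and SAEs, a difference between them could come from days observed alone, and a reader could not tell whether the second dose was better or worse tolerated. The planned follow-up table would not help. By its definition, follow-up after dose 1 is about 269 days against about 180 after dose 2, which is the reverse of the periods behind the event columns. The analyses are descriptive, so these tables are the safety result.

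**Working it through.** **Inputs.** Doses on Day 1 and Day 90 (SAP 4.4). Final visit at V3 + 180 days; visit windows -4/+7 days at V3 and -7/+14 days at V5 (SAP Appendix A). The documents give no event rates, so the first-dose percentage is an assumption, varied from 0.5% to 40%.

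**1. The plan's own duration.** (90 - 1) + 180 = 269 elapsed days, which is Day 270 when Day 1 is counted as the first day. This agrees with the stated duration of approximately 270 days.

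**2. Length of each period.** Dose 1 to dose 2: 90 - 1 = 89 days, or 85 to 96 within the V3 window. Dose 2 to final visit: 180 days, or 173 to 194 within the V5 window. Ratio: 180/89 = 2.02. Extremes: 173/96 = 1.80 and 194/85 = 2.28.

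The dose-1 period ends at dose 2 if an event is assigned to the latest preceding vaccination. SAP 7.1.3 states that rule only for missing or partial dates; none is stated for complete dates.

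**3. Crude percentages with a constant rate and no vaccine effect.** p2 = 1 - (1 - p1)^(180/89):

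| After dose 1 (assumed) | After dose 2 | Ratio |
|---|---|---|
| 0.5% | 1.0% | 2.02 |
| 1% | 2.0% | 2.01 |
| 5% | 9.9% | 1.97 |
| 10% | 19.2% | 1.92 |
| 20% | 36.3% | 1.82 |
| 30% | 51.4% | 1.71 |
| 40% | 64.4% | 1.61 |

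**4. Events that cluster after a dose.** Let b be the background percentage per 89 days and e the same extra early risk after each dose, so that p = 1 - (1 - e)(1 - b)^(t/89), with t = 89 or 180:

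- b = 5%, e = 2%: 6.9% and 11.7%, ratio 1.69.
- b = 5%, e = 5%: 9.8% and 14.4%, ratio 1.47.
- b = 10%, e = 10%: 19.0% and 27.3%, ratio 1.44.

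**5. Drop-out.** If 5% or 10% of subjects are lost evenly over the period after dose 2, mean follow-up falls to 175.5 or 171 days and the period ratio to 1.97 or 1.92. Subjects who never receive dose 2 can add up to 269 days to the first-dose column, which also narrows the gap slightly.

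**6. TDV against placebo.** Both groups have the same schedule. With equal rates the TDV/placebo ratio of percentages is 1.00 in both periods. With a true rate ratio of 1.5, and 5% of placebo subjects affected in 89 days, it is 1.48 after dose 1 and 1.46 after dose 2.

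**7. With person-time.** In the 1% row, -ln(0.99)/89 x 36,525 = 4.1 per 100 subject-years, or 4.1/12 = 0.34 per 100 subject-months. The 2.0% after dose 2 gives the same rate, so the ratio is 1.00. An equal window after each dose also gives 1.00.

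**The case against.** **The split may not apply.** The default yields to anything specified otherwise, and the whole-trial period could be such an exception. The SAP does not say, so it would be too strong to read the by-dose split of MAAEs and SAEs as explicit. It is still the more natural reading. The whole-trial phrase sits where the 28-day phrase sits for unsolicited AEs, so it sets a window; the denominator rule, placed before all these families, refers to the respective dose; and nothing limits these tables to the any-vaccination column. On the other reading, the layout is undecided and one sentence is needed to settle it.

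**An equal window already exists.** A reader might infer that none is planned for these events. Table 7.d contradicts that: its 28-day column counts MAAEs and SAEs and, if the default applies, does so by dose. What lacks a common window or person-time is the tabulation by system organ class (SOC) and preferred term (PT).

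**The endpoint and the randomized comparison are untouched.** This stands. The endpoint is a whole-trial percentage, both groups follow one schedule, and no comparison between doses is planned. A by-dose percentage is also a correct crude figure for its own period.

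**The second dose will not look twice as bad throughout.** A reader might infer a doubling by construction in all three families. The arithmetic gives about 2 only for uncommon events at a constant rate. For AEs leading to IP withdrawal the pattern fails: after dose 2 of a two-dose regimen nothing remains to withhold, so these events fall almost entirely after dose 1. AEs leading to trial discontinuation need not follow a constant rate.

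**Interview spacing does not add to the excess.** The longest gap is 60 days after dose 1 (Day 30 to Day 90) and 150 days after dose 2 (Day 120 to Day 270). Longer recall would tend to lower MAAE reporting after dose 2. SAEs rely less on interviews, because Protocol 9.3.4 asks subjects to contact the site at once about hospitalization or emergency visits.

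**Conclusion.** The point holds for MAAEs and SAEs as a matter of presentation, provided the by-dose default applies to them. Step 3's excess in the second-dose percentage, about 1.6 to 2.0 times, would then arise with no change in risk. It rests on a constant rate and an assumed first-dose percentage of 0.5% to 40%; early clustering brought it down to 1.44 in the cases tried. The SOC and PT tables carry nothing that would reveal this, because the length of the dose-1 period is not shown anywhere. The documents do not support a claim of bias in the treatment comparison or in the endpoint. The change is a cheap improvement and does not affect the primary analysis.

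**What to change.** 1. In SAP 7.11.1, state that the endpoint analysis of MAAEs and SAEs is the whole-trial summary by trial group, and say whether the by-dose split applies to them.
2. If by-dose columns are kept, choose one of two forms. Either restrict them to the 28 days after each dose already used for unsolicited AEs, including the SOC and PT tables; or keep the full periods and add, for each dose period, subject-time at risk and events per 100 subject-months.
3. In SAP 7.7, add a summary of follow-up from dose 1 to dose 2, or to the end of the trial if dose 2 is not given.
4. For subjects who miss dose 2, keep their later events and count their actual time at risk. Cutting their dose-1 time at Day 90 would remove those events from the by-dose tables.

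The cost is SAP wording and slightly more table work; all dates needed are already collected. The 28-day form leaves later events out of the by-dose columns, but they remain in the whole-trial summary.
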